
Concept and Rationale: Besides allogeneic stem cell transplantation (allo-SCT), the DNA methyltransferase inhibitor (DNMTi) azacitidine (AZA) is the only treatment proven to prolong survival in patients with higher risk myelodysplastic syndrome (HR-MDS). Nonetheless, HR-MDS patients treated with AZA have a median survival advantage of 9.5 months (24.5 vs 15 months median OS)¹ and the objective response rate is only 50% with most patients eventually relapsing within 2 years¹. Failure of DNMTi therapy occurs in the majority of treated patients and carries a dismal prognosis with a median survival of less than 6 months ². To date, no drug or combination of drugs have improved survival of MDS patients in the post-DNMTi failure setting in randomized trials, and there is currently no standard of care for those patients. Therefore, improving outcomes of MDS patients after failure of DNMTi remains a top clinical and research priority ³.
 
Histone deacetylase inhibitors (HDACi) comprise a group of drugs that share the ability to inhibit the important epigenetic eraser enzymes HDACs. As single agents, several HDACi exhibited only modest clinical activities in MDS^{4,5}. Therefore, the interest to develop these agents further has focused on combination-based strategies, usually with DNMTi. To date, no HDACi-DNMTi combination has improved survival of MDS patients in randomized studies when used in the frontline or the post-DNMTi failure setting. These observations suggest that while HDACi therapy has modest activity in MDS, DNMTi might not be the best choice for combination-based regimen with HDACi. Exploration of alternative agents to combine with HDACi in the post-DNMTi failure setting might be a more rational approach.
 
Recent advances in tumor immunology have facilitated understanding the role of immune escape as important mechanism of cancer progression and treatment resistance. One important mechanism which cancers employ commonly to evade the immune system involve the exploitation of T-cell inhibitory pathways and molecules such as the programmed death-1 (PD-1) and cytotoxic T-lymphocyte associated antigen-4 (CTLA-4) ^{6,7}. Immune checkpoint blockade with antibodies directed against PD-1, its ligand (PD-L1), and CTLA-4 has emerged as promising approaches to reverse immune evasion, and have resulted in a significant and durable clinical activity in some patients with advanced solid malignancies especially metastatic melanoma, lung cancer, bladder cancer, and Hodgkin disease ⁸⁻¹¹. Compared to expanding clinical applications of immune checkpoint inhibitors in solid tumors, the mechanisms of immune evasion in hematologic malignancies including MDS have not been fully elucidated. Several studies suggest that interaction between PD-1 and PD-L1 may induce immune evasion in MDS¹² and moreover the upregulation of these molecules could be associated with resistance to DNMTi therapy in MDS¹³.
 
Furthermore, recent studies suggest that myeloid-derived suppressor cells (MDSCs), which are significantly increased in bone marrows of MDS patients (~35% vs <5% in non-MDS bone marrow), play an important role in ineffective hematopoiesis in MDS¹⁴. MDSCs also induce resistance to immune checkpoint blockade (anti-CTLA4 and anti-PD1) in colon cancer bearing mice¹⁵. Importantly, in this mouse model MDSCs were significantly decreased by the use of the epigenetic modulator entinostat (ENT), leading to rejection of tumors when combined with immune checkpoint blockade¹⁵.
 
Primary Objective(s): To identify the maximum tolerated total dose (MTD) of entinostat given in combination with pembrolizumab (MK-3475) in post-HMA failure setting for patients with MDS.
 
Secondary Objective(s): To obtain a preliminary estimate of efficacy of entinostat in combination with pembrolizumab (MK-3475).


Primary Endpoint(s): MTD as defined by the occurrence of dose-limiting toxicity (DLT) among 2 dose schedules
Secondary Endpoint(s): Overall response rate (ORR), with a target if at least 15% to be continued for a phase 2 study.
Exploratory Endpoint(s):

Median response duration for responders, median time of progression to AML, median overall survival (OS) and 1- and 2-year OS rates.Assessment of the dynamic quantitative change in proportion of MDSCs and PD-1 expression in BM with combined therapy and correlation with any observed clinical responses.
Study Design: This will be a phase 1b study [see schema]. The proposed dosing of ENT has been

previously tested in MDS as single agent and shown to be well-tolerated. While the combination of ENT with the anti-PD1, pembrolizumab (MK-3475) has not been studied clinically in MDS patients, based on mechanisms of action it is unlikely that this combination would have overlapping toxicities.

PART 1: ENT has been previously evaluated as a single agent therapy in patients with MDS at these doses and has been well tolerated. The ENT monotherapy run-in part (cycle 1) will allow to study the changes in MDSCs at pre- and post- ENT treatment (the end of cycle 1) to dissect the effects of ENT monotherapy from those of the combined ENT/anti-PD1 therapy.

We will perform '3+3' classical dose escalation design to determine DLT. The first 3 patients will receive ENT at dose level 1 (DL1: 8mg on D1, 8 of 21-day cycles). pembrolizumab (MK-3475) will be added starting day 1 cycle 2 at the approved dose (200mg intravenously [IV] over 30 minutes on D1 of 21-day cycles) for 4 cycles. A safety committee that includes the study chair, the principal investigator from any study site that has enrolled a patient on the specific DL, as well as two sub-investigators from Yale will review safety data after enrollment of every 3 patients during the dose escalation phase. The committee will have the discretion to decide to enroll 3 more patients in the specific dose level even if no DLT occurred in the first 3 treated patients in that dose level if there are toxicity/safety concerns that did not qualify as DLT (maximum of 6 evaluable patients to be enrolled at any dose level). The committee can also decide to enroll patients at a lower dose level after the first 3 or after the first 6 patients enrolled in any dose level even if no or one DLT occurred at that dose level if there are toxicity/safety concerns that did not qualify as DLT. The following regarding enrollment in different dose levels will be considered guidance for the safety committee but can be modified in accordance of above: If no patient of the 3 patients treated with combined therapy at DL1 develops DLT, then dose level 2 (DL2) will be tested. DL2 will be with ENT at 8mg on D1, 8 and 15 and pembrolizumab (MK-3475) at 200mg IV on D1 of 21-day cycles. If 1 patient out of the 3 patients has DLT at DL1, we will expand cohort to 3 more patients and if 1 patient of the 6 patients has DLT (i.e. only 0/3 or 1/6), we will test next dose (DL2). If no patient of the 3 patients treated with combined therapy at DL2 develop DLT, then DL2 will be used for part 2 (expansion cohort). If 1 patient out of the 3 patients has DLT at DL2, we will expand cohort to 3 more patients and if 1 patient of the 6 patients has DLT (i.e. only 0/3 or 1/6), dose level 2 (DL2) will be used for part 2 (expansion cohort). If 2 patients or more of the 6 patients at DL2 experience DLT, DL1 will be used for expansion cohort. The cycle duration will be 21 days, the maximum number of treatment cycles of entinostat will be 18 cycles and for pembrolizumab (MK-3475) the maximum number of cycles will be 17. Cycle 2 to cycle 18, will have concurrent administration. In all the phases of the study, entinostat will be administered in clinic within 2 hours before administration of pembrolizumab (MK-3475). Entinostat will be stored at the pharmacy and it will not be given for the patient to take home.

An additional dose level (DL -1) in which day 8 of ENT will be omitted (i.e. ENT at 8mg on D1, and pembrolizumab (MK-3475) at 200mg IV on D1 of 21-day cycles) will be used if 2 or more patients develop DLT during the first 2 cycles of combined therapy at DL1. If 0 or 1 patients of the 6 patients treated with combined therapy at DL-1 develop DLT then DL-1 will be used in the second part of the study. If 2 or more 6 patients enrolled in DL -1 develop DLT, then the study will be terminated. If the AE drug causality is clear (e.g. immune related event) and one of the drugs is discontinued, the patient can remain on the study and receive the non-causative agent.

Toxicities will be tabulated and graded according to the Common Terminology Criteria for Adverse Events Version 5 (CTCAE-5). DLT will be assessed after the first 2 cycles of combined therapy. Responses will be as defined by International Working Group (IWG)-2006 criteria (CR, PR, or HI) and

[figure not shown]
assessed at the end of combined first 2 cycles, and every 2 cycles afterwards. Patients who achieve an objective response or maintain a stable disease (SD) status after the first 4 combination cycles will continue receiving both drugs at the same schedule till progression or up to 1 year of combined therapy.

PART 2: After the safe dose of the combination is established, 15 patients will be treated with ENT+ pembrolizumab (MK-3475) combination at that same dose and schedule. Participants who go off-study during the 1st cycle of entinostat will be replaced in the escalation phase. Participants who do not complete the first 2 cycles of combined therapy without experiencing a DLT (as DLT period is defined in the first 2 combined therapy cycles) during dose escalation will also be replaced. To be DLT-evaluable, the patient must complete the first two cycles of combined therapy without experiencing a DLT. Any patient who is dose reduced during the entinostat run-in first cycle due to entinostat-related toxicity will be analyzed on the dose level that corresponds to the reduced dose level delivered during the first cycle of combined therapy.

[figure not shown]
Assessment of response will occur after 4 combination cycles and similar to part 1, those who achieve an objective response or SD will continue to receive the therapy till progression. Patients who progress or respond and subsequently lose response will be withdrawn from study. BM biopsy/aspirate and PB samples will be done at baseline, after first cycle of ENT monotherapy, every 2 cycles of combined therapy, and at time of progression or study discontinuation. Formal safety assessment will be performed at end of DLT-observing period (i.e. 1 ENT monotherapy cycle and 2 cycles of combined therapy) for each patient) for each DL to assess for any unexpected autoimmune or other toxicity. The cycle duration will be 21 days, the maximum number of treatment cycles of entinostat will be 18 cycles and for pembrolizumab (MK-3475) the maximum number of cycles will be 17. Cycle 2 to cycle 18, will have concurrent administration.

The following early stopping rule for excess toxicity in the expansion cohort will be used: We will cease enrollment in the expansion phase at the dose determined from dose escalation part of the study if we observe two or more DLTs among the first six evaluable patients enrolled in the expansion cohort. An evaluable patient is any patient who received a study drug. If the true toxicity rate is 50% or greater at the MTD then this rule will stop the trial with probability at least .89. Similarly, if the true toxicity rate is 33% at the MTD then this stopping rule will end the trial with probability .65. In that event, a new expansion cohort will start at the dose level immediately below the dose level that was expanded. If the dose level being expanded is dose level -1, then the study will be terminated.

Study Schema

Study design

Dose Escalation Schedule		
Dose Level	Dose*	
	Entinostat	Pembrolizumab
Level -1(Backup dose level)	8mg po D1	200mg
Level 1 (starting dose level)	8mg po D1,8	200mg
Level 2	8mg po D1,8,15	200mg

Number of Patients: 6-27

Main Criteria for Inclusion/Exclusion:

Pathologically confirmed MDS diagnosis (regardless of initial IPSS risk category) or oligoblastic AML with 21-30% BM blasts in whom DNMTi have failed. Patients who have developed AML after DNMTi therapy can be enrolled as long as they have initiated DNMTi therapy while they were in the MDS or oligoblastic AML (20-30% BM blasts) phase and the study chair agrees. Failure of DNMTis is defined as: Failure to achieve a CR, PR or HI after at least 4 cycles of DNMTi or progressed after such therapy.

The patients should also have

- ECOG performance status of 0, 1, or 2 at study entry
- Laboratory test results within these ranges:
Calculated creatinine clearance by MDRD (CrCl) =>60 ml/min/1.73 squared meter
- Total bilirubin \leq 2.0 mg/dL unless due to Gilbert's syndrome, hemolysis, or ineffective hematopoiesis and AST (SGOT) and ALT (SGPT) \leq 3 x ULN Females of childbearing potential must have a negative serum or urine pregnancy test within 72 hours prior to start of first cycle of therapy.
- Patients must have no clinical evidence of CNS or pulmonary leukostasis, disseminated intravascular coagulation, or CNS leukemia.
- Patients must have no serious or uncontrolled medical conditions
 - Patients, who relapsed 6 months after bone marrow transplant and have no evidence of active graft versus host disease and are off systemic immunosuppressant medications for at least 2 months and have received HMA therapy before or after transplant and meet other eligibility criteria of progression after at least 4 months of DNMTi therapy, are eligible to be enrolled in this clinical trial.

Exclusion criteria:

- Any patients eligible for allo-SCT and willing to undergo allo-SCT as determined at time of screening for trial. Patients who are ineligible or not interested in undergoing allo-SCT will be eligible for the trial.
- Any serious medical condition, uncontrolled intercurrent illness (e.g., active infection, symptomatic congestive heart failure (CHF), unstable angina, cardiac arrhythmias, laboratory abnormalities, or psychiatric illness and/or biopsychosocial conditions that may limit

compliancePatients with known active cancers who are receiving active therapy

- Patients with a known positive test for hepatitis B virus surface antigen (HBV sAg) or hepatitis C virus ribonucleic acid (HCV antibody) indicating acute or chronic infection might be enrolled if the viral load by PCR is undetectable with/without active treatment.
- Pregnant or breast-feeding females (lactating females must agree not to breast feed while taking the study drugs)
- Use of any other experimental drug or therapy within 21 days of baseline - patients who have had chemotherapy or radiotherapy within 4 weeks of entering the study or those who have not recovered from adverse events due to agents administered more than 4 weeks earlier
- Known hypersensitivity to pembrolizumab (MK-3475) or entinostat or history of allergic reactions to compounds of similar chemical or biologic composition to anti-PD1 antibodies or entinostat.
- Prior treatment with any anti-PD-1 blocking therapies or HDACi, or anti-CTLA-4 antibody, CD137 agonist or other immune activating therapy such as anti-CD 40 antibody within the last 3 months of enrollment in the study.
- Any history of active or severe autoimmune disease including:
 - Inflammatory bowel disease, including ulcerative colitis and Crohn's Disease
 - Rheumatoid arthritis, systemic progressive scleroderma, systemic lupus erythematosus, autoimmune vasculitis (e.g., Wegener's Granulomatosis).
 - Note: patients with hypothyroidism who are on stable doses of hormone replacement therapy are allowed
- CNS or motor neuropathy considered of autoimmune origin (e.g. Guillain-Barre Syndrome, myasthenia gravis, multiple sclerosis)

Has a history of (non-infectious) pneumonitis that required steroids or has current pneumonitisPatients who are Human Immunodeficiency Virus (HIV) positive may participate IF they meet the following eligibility requirements: They must be stable on their anti-retroviral regimen, and they must be healthy from an HIV perspective.

They must have a CD4 count of greater than 250 cells/mcL.

They must not be receiving prophylactic therapy for an opportunistic infection.

Intervention and Mode of Delivery: Entinostat, PO administration, pembrolizumab (MK-3475), IV infusion

Duration of Intervention and Evaluation: 1 year or until disease is progressed

Statistical Methods:

(a) Definition of primary outcome/endpoint: The primary endpoint is the maximum tolerated dose (MTD), which is the highest dose level where 1 or fewer of 6 participants experience a dose limiting toxicity (DLT) during the first two cycles of treatment. The RP2D is the same as the MTD. The maximally administered dose is the dose at which two or more of 6 participants experience a DLT.

Definition of DLT: DLT will be defined as the occurrence of any of the following during the first 2 cycles of combined therapy unless the event can clearly be determined to be unrelated to the study drugs.

- Any grade 3 or 4 non-hematologic toxicity with the following exceptions: A) Transient laboratory abnormalities that can be treated or resolve to grade 2 or less within 72 hours.
- Grade 4 hematologic toxicity, including treatment-associated aplasia lasting >42 days from the last dose of study drug. Given that severe anemia, neutropenia and thrombocytopenia are features of advanced MDS and commonly encountered in this patient population, they will not be used to define DLT except if associated with prolonged treatment-associated aplasia as described above.
- Patients with grade 3 immune related adverse events will be removed from the treatment and this will be considered to be a DLT as well as any other immune-related adverse event that results in pembrolizumab interruption, dose modification, or discontinuation of therapy.
-
- Definition of secondary outcomes/endpoints: Overall response rate (ORR: The sum of rates of complete response [CR], partial response [PR], and hematologic improvement [HI]) as defined by the modified IWG-2006 criteria (**Appendix A**) with a goal of at least 20% to be considered clinically meaningful for further evaluation in larger studies.
- Analytic plan for primary objective: Toxicities will be tabulated and graded according to the Common Terminology Criteria for Adverse Events Version 5 (CTCAE-5). DLT will be assessed after the first 2 cycles of combined therapy.
- Analytic plan for secondary objectives/ Sample size justification: Currently there is no therapy that has been shown to prolong survival in MDS in the post-DNMTi setting and that the expected best response in patients receiving supportive care only in post-DNMTi setting is negligible (1% or less). It is generally accepted that a $\geq 15\%$ ORR in the post-DNMTi is clinically meaningful and would be worth further evaluation in larger studies. We therefore calculated that treating a total of 21 patients in the combination arm (6 in the first part of the study and 15 in the second part of the study) to test the difference of ORR between 1% (null hypothesis-supportive care only) and 15% (alternative hypothesis, combination therapy). The null hypothesis response rate of 1% will be rejected if we observe 2 or more favorable responses. This criterion has significance level between .02 and .03 using a one-sided binomial test. The criterion has power between .84 and .93 for testing an alternative response rate of 15%.
- The total number of patients enrolled in the study will range from 6 to 27.
- Analytic plan for exploratory objectives: The quantitative change in MDSCs (% MDSCs by

flow cytometry, QIF score by AQUA) during treatment with the ENT/anti-PD1 combined therapy will be estimated using mixed effects models to take into account the within-patient correlation. Likelihood ratio tests will be performed to confirm if random intercepts and slopes are necessary in the model. The fixed effect for change in MDSCs over time will be evaluated for significance. The variability in the rate of change in MDSCs across patients will also be examined. The association between the clinical outcome and a meaningful reduction in MDSCs, which will be defined after a review of the data, will be assessed with the chi-square test. The quantity of MDSCs at baseline and during treatment as continuous variables can also be compared between responding and non-responding patients using a t-test or Mann-Whitney U-Test, if more appropriate.

TABLE OF CONTENTS

SCHEMA	2
TABLE OF CONTENTS	10
1. OBJECTIVES	13
1.1 Primary Objectives.....	13
1.2 Secondary Objectives.....	13
1.3 Exploratory objectives	13
2. BACKGROUND	13
2.1 Myelodysplastic syndrome (MDS)	13
2.2 CTEP IND Agents.....	16
2.3 Rationale for combining anti-PD1 antibody with entinostat in MDS after DNMTi failure	21
2.4 Correlative Studies Background (full correlative proposal attached in Appendix J).....	21

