5.1.3 Other Modality(ies) or Procedures: N/A

5.2 **Definition of Dose-Limiting Toxicity**

The primary endpoint is the maximum tolerated dose (MTD), which is the highest dose level where 1 or fewer of 6 participants experience a dose limiting toxicity (DLT) during the first two combined cycles of treatment. The recommend phase 2 dose (RP2D) is the same as the MTD.

NCI Protocol #:10009

Version Date: 09/04/2020

The maximally administered dose is the dose at which two or more of 6 participants experience a

DLT.

DLT will be defined as the occurrence of any of the following during the first 2 cycles of combined therapy unless the event can clearly be determined to be unrelated to the study drugs.

- Any grade 3 or 4 non-hematologic toxicity with the following exceptions: A) Transient laboratory abnormalities that can be treated or resolve to grade 2 or less within 72 hours.
- Grade 4 hematologic toxicity, including treatment-associated aplasia lasting >42 days from the last dose of study drug. Given that severe anemia, neutropenia and thrombocytopenia are features of advanced MDS and commonly encountered in this patient population, they will not be used to define DLT except if associated with prolonged treatment-associated aplasia as described above.
- Patients with grade 3 immune related adverse events will be removed from the treatment and this will be considered to be a DLT as well as any other immune-related adverse event that results in pembrolizumab interruption, dose modification, or discontinuation of therapy.

Participants who do not complete the first 2 cycles of combined therapy without experiencing a DLT (as DLT period is defined in the first 2 combined therapy cycles) during dose escalation will also be replaced. To be DLT-evaluable, the patient must complete the first two cycles of combined therapy without experiencing a DLT. Any patient who is dose reduced during the entinostat run-in first cycle due to entinostat-related toxicity will be analyzed on the dose level that corresponds to the reduced dose level delivered during the first cycle of combined therapy.

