5.5 Duration of Therapy

In the absence of treatment delays due to adverse event(s), treatment may continue for one year (maximum 18 cycles or entinostat and maximum 17 cycles of pembrolizumab (MK-3475)) or until one of the following criteria applies:

- Disease progression as defined in modified IWG-2006 ([Appendix A1](#), [Appendix A2](#)) for MDS
- If disease has shown evidence of progression based on an increase in the blast counts according to the modified IWG-2006, but the patient is otherwise clinically stable and his transfusion requirement have not changed, the investigator can give two additional cycles of combined treatment and bone marrow biopsy will be repeated after that cycle. If repeat bone marrow biopsy confirms disease progression, the patient will be taken off the trial.
- Intercurrent illness that prevents further administration of treatment
- Patient decides to withdraw from the study
- General or specific changes in the patient's condition render the patient unacceptable for further treatment in the judgment of the investigator

- Clinical progression
- Patient non-compliance
- Pregnancy
 - All women of child bearing potential should be instructed to contact the investigator immediately if they suspect they might be pregnant (e.g., missed or late menstrual period) at any time during study participation.
 - The investigator must immediately notify CTEP in the event of a confirmed pregnancy in a patient participating in the study.
- Termination of the study by sponsor
- The drug manufacturer can no longer provide the study agent
- Unacceptable adverse event(s), including:
 - Any Grade 2 drug-related uveitis or eye pain or blurred vision that does not respond to topical therapy and does not improve to Grade 1 severity within the re-treatment period OR requires systemic treatment.
 - Grade 3 drug-related autoimmune or inflammatory event including uveitis, pneumonitis, diarrhea, colitis, neurologic adverse events, hypersensitivity reaction, or infusion reaction of any duration requires discontinuation.
 - Any Grade 3 or 4 drug-related laboratory imbalance or electrolyte abnormality, not associated with underlying organ pathology and that do not require treatment except for electrolyte replacements, do not require treatment discontinuation, with the following exceptions with approval of the Principal Investigator:

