5.7 Criteria for Removal from Study

Patients will be removed from study when any of the applicable criteria, including progressive disease, withdrawal, or inability to follow study protocol as listed in [Section 5.5](#). The reason for study removal and the date the patient was removed must be documented in the Case Report Form.

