5.11 Treatment Up to 1 Years

Treatment with entinostat and pembrolizumab (MK-3475) will continue for up to one year of combined therapy administered, documented disease progression, unacceptable adverse event(s), intercurrent illness that prevents further administration of treatment, investigator's decision to withdraw the patient, patient withdraws consent, pregnancy of the patient, noncompliance with trial treatment or procedure requirements, or administrative reasons.

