6. DOSING DELAYS/DOSE MODIFICATIONS

Although entinostat and pembrolizumab (MK-3475) have distinct toxicity profiles, they do share some AEs such as fatigue and nausea. There is the theoretical possibility that 1 agent may potentiate the other and hence drug causality will not always be clear. In the event of uncertainty, dose reductions and/or delays will follow the most conservative approach (i.e., delays and/or dose reductions for both drugs) until resolution of the event. No dose reductions will be performed for pembrolizumab (MK-3475). Guidance for delays and or dose reductions for entinostat are presented.

6.1 Entinostat Dose Modifications and Supportive Care Guidelines for Drug-Related Adverse Events

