Grades 3 or 4 Grade 3: Prolonged (i.e., not rapidly responsive to symptomatic medication and/or brief interruption of infusion); recurrence of symptoms following initial improvement; hospitalization indicated for other clinical sequelae (e.g., renal impairment, pulmonary infiltrates) Grade 4: Life-threatening; pressor or ventilatory support indicated	
Stop Infusion.
 
Additional appropriate medical therapy may include but is not limited to:
 
 IV fluids Antihistamines NSAIDS Acetaminophen Narcotics Oxygen Pressors Corticosteroids Epinephrine 
Increase monitoring of vital signs as medically indicated until the subject is deemed medically stable in the opinion of the investigator.
 
Hospitalization may be indicated.
 
Subject is permanently discontinued from further trial treatment administration.
	No subsequent dosing
Appropriate resuscitation equipment should be available in the room and a physician readily available during the period of drug administration.		
For Further information, please refer to the Common Terminology Criteria for Adverse Events v4.0 (CTCAE) at http://ctep.cancer.gov		

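### The documents contradict themselves on whether a patient with a grade 3 immune-related event may continue on the other drug

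*Combined protocol and SAP*

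**What the plan says.** Four places bear on the same patient.

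- Synopsis, Study Design, Part 1. The option opens with "If the AE drug causality is clear (e.g. immune related event" and goes on to say that if "one of the drugs is discontinued, the patient can remain on the study and receive the non-causative agent". It sets no grade limit and no limit on cycles.
- Synopsis, definition of DLT, and Section 5.2, in the same words: "Patients with grade 3 immune related adverse events will be removed from the treatment and this will be considered to be a DLT". Neither place says which drug the patient is removed from.
- Section 5.5, under unacceptable adverse events, lists "Grade 3 drug-related autoimmune or inflammatory event including uveitis, pneumonitis" and other such events as requiring discontinuation, whatever their duration. The drug is not named.
- Section 5.7 refers back to 5.5: "Patients will be removed from study when any of the applicable criteria" listed there is met.

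The parallel design text in Sections 5.1 and 13.1 repeats the dose-level paragraph of the synopsis but leaves out the single-drug sentence. Section 6 deals only with unclear causality: "In the event of uncertainty, dose reductions and/or delays will follow the most conservative approach (i.e., delays and/or dose reductions for both drugs". The general immune-event table in Section 6.2.3 withholds pembrolizumab for grade 3 and 4 events and says nothing about entinostat.

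**The concern.** Immune-related events are an expected toxicity of pembrolizumab, and the synopsis uses them as its example of clear causality. A grade 3 event of this kind is therefore where the single-drug option and the removal rules are most likely to meet. One text keeps the patient on study and on entinostat, another removes the patient from a treatment it does not define, and a third removes the patient from the study.

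At stake are the entinostat exposure after the event, the time the patient stays under on-treatment observation, and consistency between sites. Marrow assessments are scheduled by treatment cycle, so the section a site follows also affects how long response continues to be assessed on schedule.

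**Working it through.** **Inputs.** The maxima are 18 entinostat cycles and 17 pembrolizumab cycles, with cycles of 21 days and pembrolizumab starting in cycle 2 (synopsis; Section 5.1). The DLT window is the first two combined cycles, which are study cycles 2 and 3 (Section 5.2).

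**Cycle count.** Further entinostat cycles = 18 - cycle in which pembrolizumab stops.

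- Stop in cycle 2: 18 - 2 = 16 cycles, or 16 x 21 = 336 days.
- Stop in cycle 3: 18 - 3 = 15 cycles, or 15 x 21 = 315 days.

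**Side by side.** Take a patient with a grade 3 immune-related event in cycle 2 that is clearly due to pembrolizumab, with pembrolizumab stopped.

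| Text followed | Status | Further entinostat cycles |
|---|---|---|
| Synopsis, Part 1 | May stay on study | Up to 16 |
| Synopsis DLT definition and 5.2, if only pembrolizumab is meant | Off pembrolizumab | Up to 16 |
| Synopsis DLT definition and 5.2, if both drugs are meant | Off all treatment | 0 |
| 5.5 with 5.7 | Removed from study | 0 |
| 5.1 and 13.1 | Option not mentioned | Not stated |

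The clearest clash is between the first and fourth rows, because remaining on the study and removal from it cannot both apply. The 5.5 rule is also not confined to the DLT window, so it covers the whole treatment period. Other items in the 5.5 list name pembrolizumab; this one does not. Because the DLT sentence is in the synopsis too, the synopsis is unclear within itself.

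**What does not change.** Within the window, a grade 3 immune-related event counts as a DLT under Section 5.2 whatever the patient receives next, so the conflict does not alter the DLT count.

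**Response-rate rule.** Section 13.2 rejects a 1% rate on 2 or more responses among 21 to 27 patients and states a one-sided level of .02 to .03 and power of .84 to .93 at 15%. The formula is P(2 or more) = 1 - (1-p)^n - n p (1-p)^(n-1).

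- n = 21: level 0.0185, power 0.845.
- n = 27: level 0.0297, power 0.928.

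The stated figures reproduce and are not in dispute.

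**The case against.** Several points on the other side have force.

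*The treatment* in Section 5.2 may mean pembrolizumab alone: the same sentence goes on to speak of pembrolizumab interruption or modification, and Section 6 gives the two drugs separate rules. That reading is possible and would remove the clash with 5.2. It is not stated, and it leaves 5.5 with 5.7 in place.

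The absence of the option from 5.1 and 13.1 is silence, not contradiction. Their sentence about continuing both drugs concerns patients with response or stable disease after four combination cycles, and the synopsis carries that sentence alongside the option. This stands.

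A reader might infer that Section 6.2.5 ends both drugs after a grade 3 or 4 infusion reaction: "Subject is permanently discontinued from further trial treatment administration". The documents do not establish this. The table lies in the pembrolizumab part of Section 6, and Section 5.1.1 uses *trial treatment* for pembrolizumab alone. The term needs defining, but a conflict is not shown.

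Sixteen cycles is a ceiling. It means 336 days without progression, against the median survival of 5 months cited in Section 5.6.

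A reader might also infer that single-drug responses would invalidate the response-rate test, since only two responses are needed and Section 2.1 credits entinostat with modest activity in MDS. The documents do not support that.

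- Section 13.5.2 deliberately keeps all eligible patients in the main response analysis, whatever the irregularities in drug administration.
- The null is supportive care, not entinostat alone. A response driven by entinostat during combined dosing counts as well, so barring later responses would not settle attribution.
- Neither the number of single-drug patients nor a single-agent response rate in MDS is given. Assuming 1 to 4 such patients responding at 5% to 15%, and all others at 1%, the chance of 2 or more responses is 0.025 to 0.174 at n = 21 and 0.038 to 0.197 at n = 27. Those results come from the assumptions, not from the plan.
- Restricting which responses count could discard true combination responses, given the pembrolizumab half-life of about 4 weeks (Section 2.1.2.1). If 1 to 4 such patients were counted as non-responders, power at 15% would fall from 0.845 to between 0.824 and 0.748 at n = 21, and from 0.928 to between 0.918 and 0.880 at n = 27.

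**Conclusion.** The contradiction is real for grade 3 immune-related events and should be corrected. It is firmest between the synopsis option and Section 5.5 read with 5.7. In Section 5.2 and the synopsis DLT definition it is an ambiguity that becomes a contradiction if both drugs are meant. For other clearly attributed toxicities the body of the protocol is mostly silent, and no wider conflict is claimed.

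The size is up to 16 further entinostat cycles against none for a patient stopping pembrolizumab in cycle 2, or 15 against none in cycle 3. These are upper limits that assume no progression, no other reason to stop, and the 18-cycle maximum applying to entinostat given alone. The documents do not say how many patients would be affected. The DLT count and the stated level and power of the response-rate rule are unaffected.

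**What to change.** The sponsor should reconcile the synopsis (Study Design, Part 1, and the DLT definition) with Sections 5.2, 5.5 and 5.7. Each should state whether treatment, discontinuation and removal refer to pembrolizumab, to entinostat or to both, and whether the patient stays on study. The reconciled wording should then go into Sections 5.1 and 13.1, and Section 6.2.5 should say whether *trial treatment* there means pembrolizumab only. Which rule to adopt is a clinical decision for the sponsor; none is proposed here.

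Keep the main response-rate analysis on all eligible patients, as in Section 13.5.2, and leave the test unchanged. If single-drug continuation is retained, add to Section 13.4 a descriptive listing of responses first documented while the patient was on one drug.

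The cost is a wording amendment and, if the listing is added, one derived flag in the response data. Sample size, level and power do not change.
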